## **Study Population**

The study population will consist of males and females aged 12 to 75 years (inclusive) with EGE. Approximately 45 adults (aged 18 to 75 years) and adolescents (aged 12 to 17 years) with a weight of  $\geq 30$  kg will be enrolled in the study.

## **Length of Study**

The maximum duration of subject participation in the Screening Period, Induction and Maintenance Phases is approximately 72 weeks, including the Interim and the Final Safety Follow-

up Visits. Subjects will participate for up to 4 weeks in the Screening Period (the screening EGD may be completed up to 8 weeks prior to Day 1), 16 weeks in the Induction Phase, and 32 weeks in the Maintenance Phase of the study. Subjects completing the Maintenance Phase who do not continue IP administration in the OLE Phase will complete the Interim and the Final Safety Follow-up Visits (at 8 and 16 weeks) after final IP administration.

Subjects entering the OLE Phase at Induction Phase Week 16, during the Maintenance Phase or at Maintenance Phase Week 48 will receive weekly doses of CC-93538 during the OLE Phase for a minimum of 2 years or as long as they continue to participate while the study is active, will complete an Early Termination Visit or an End of Treatment Visit within 2 weeks after the final dose, and complete the two Safety Follow-up Visits at 8 and 16 weeks after the final dose. Subjects may participate in the OLE Phase as early as 16 weeks after beginning enrollment in the Induction Phase or as late as following Week 48 of the Maintenance Phase. Individual subject participation in the OLE Phase may be a minimum of 2 years but may extend for a longer duration, provided the subject does not withdraw from the OLE Phase prior to Year 2 of the OLE. The terms “this study” in this protocol will automatically be replaced with “post-marketing clinical study” on and after the date of marketing approval in Japan.

The End of Trial is defined as either the date of the last visit of the last subject to complete the post-treatment follow-up (the Final Safety Follow-up Visit), or the date of receipt of the last data point from the last subject that is required for primary, secondary [REDACTED] analysis, as prespecified in the protocol, whichever is the later date.

## **Study Treatments**

Subjects will be randomized 2:1 to the following treatment arms for the 16-week Induction Phase:

- CC-93538 360 mg SC once weekly for 16 weeks
- Matching placebo SC once weekly for 16 weeks

Subjects who are randomized to receive CC-93538 360 mg SC once weekly in the Induction Phase will be re-randomized 1:1 to the following treatment arms for the 32-week Maintenance Phase:

- CC-93538 360 mg SC once weekly for 32 weeks
- CC-93538 360 mg SC once every other week for 32 weeks. During the Maintenance Phase, matching placebo will be administered once every other week on alternate weeks to maintain the blind.

Subjects who are randomized to receive matching placebo in the Induction Phase will continue the following treatment arm.

- Matching placebo SC once weekly for 32 weeks

The CC-93538 360 mg SC dose will be administered by 2 injections of 1.2 mL each provided in 150 mg/mL pre-filled syringes (PFS) during the Induction Phase and the Maintenance Phase.

Subjects entering the OLE Phase will receive the following treatment:

- CC-93538 360 mg SC once weekly during the OLE treatment period

For the OLE Phase, all subjects will receive CC-93538 360 mg SC once weekly during the OLE Phase. The 360 mg dose of CC-93538 will be administered by a single injection of the 360 mg/2 mL [REDACTED] at a concentration of 180 mg/mL CC-93538. All subjects currently in the OLE Phase will start receiving a single injection of the 360 mg/2 mL [REDACTED] once Protocol Amendment 5 is implemented, informed consent is obtained, and IP is available on-site. For currently enrolled subjects, a switch to the new [REDACTED] presentation will occur at the next regularly scheduled study visit or at a First [REDACTED] Administration Visit in case the next scheduled protocol visit is not within 4 weeks of Protocol Amendment 5 site approval, once the IP is available on site. This First [REDACTED] Administration Visit is added to expedite the switch to the new [REDACTED] presentation.

The dosing regimen for the OLE may be revised, via an amendment to the protocol, after results from the core Induction Phase and Maintenance Phase are available and the most effective and safest dosing regimen is confirmed.

### **Overview of Key Efficacy Assessments**

- Enumeration of gastric and/or duodenal eos count (peak gastric and/or duodenal eos count) by analysis of hematoxylin and eosin (H&E) stained gastric and/or duodenal biopsies
- Gastrointestinal symptom score using the PRO questionnaire (Izumo Scale)

### **Overview of Key Safety Assessments**

- Type, frequency, severity, seriousness, and relationship of AEs to IP
- Clinically significant changes in vital signs, physical examinations, and laboratory findings
- Presence of and clinical consequences of anti-drug antibodies (ADAs)

### **Statistical Methods**

The primary population for assessing efficacy will be the intent-to-treat (ITT) population which consists of all randomized subjects regardless of whether or not the subject received IP (CC-93538 or placebo).

Analysis details not explained in the statistical section of the protocol will be provided in the Statistical Analysis Plan (SAP).

### Sample Size

The sample size is based on two-sample t-test for the primary endpoint, changes in mean number of peak eos per hpf in GI biopsies from baseline to Week 16. The null hypothesis and the alternative hypothesis for the primary endpoint are as follows;

- Changes in mean number of peak eos from baseline at Week 16

Null hypothesis  $H_0: \mu_{CC-93538} = \mu_{Placebo}$

Alternative hypothesis  $H_a: \mu_{CC-93538} \neq \mu_{Placebo}$ ,  
where  $\mu_{CC-93538}$  represents the true mean change value relative to CC-93538 and  $\mu_{Placebo}$  represents true mean change value relative to placebo.

Using this hypothesis, if the expected mean change in eos count in the active treatment group was -70, the expected mean change in eos count in the placebo group was 0, and the standard deviation (SD) was 70, the sample size necessary to achieve at least 80% power in a t-test at a significance level of 0.05 was calculated. Using a 2:1 ratio of active to placebo, 39 subjects are required. Assuming a Week 16 drop-out rate of approximately 10%, the goal is to enroll a total of 45 subjects.

### Primary Analysis

The primary analysis will be conducted on the ITT population based on an analysis of covariance (ANCOVA) model with treatment group, concomitant steroid use (yes or no), and baseline eosinophil count included in the model. The comparison between CC-93538 360 mg SC once weekly and placebo for change in eos count from baseline at Week 16 will be made using the difference in least squares mean (LSM) at a 5% 2-sided significance level. Point estimates for the mean difference between the two treatment groups using the LSM changes and corresponding 95% Wald confidence intervals (CI) will be reported. In addition, LSM (standard error [SE]), arithmetic means (SD), and arithmetic mean changes (SD) will be summarized by treatment group.

### Multiplicity Adjustment

Only one formal statistical test will be performed for the primary endpoint. For any other comparisons, nominal p-value (without adjustment for multiplicity) will be provided as a measure of the strength of association between the endpoint and the treatment effect rather than a formal statistical test. Therefore, the multiplicity adjustment is not applicable in this study.

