## Objectives

The primary objective of the study is to assess the efficacy of CC-93538 versus placebo in obtaining histologic improvement based on tissue eosinophil (eos) count in EGE at Week 16.

The secondary objectives are:

- To assess the efficacy of CC-93538 versus placebo in reducing EGE-related symptoms at Week 16
- To assess the efficacy and the persistence of effect of CC-93538 versus placebo at 48 weeks in:
  - Obtaining histologic improvement based on tissue eos count in EGE
  - Reducing EGE-related symptoms
- To assess the persistence of effect of CC-93538 through administration of a less frequent dosing regimen at 48 weeks in:
  - Obtaining histologic improvement based on tissue eos count in EGE
  - Reducing EGE-related symptoms
- To evaluate the safety and tolerability of CC-93538 including characterization of the immunogenicity profile
- To evaluate the efficacy and the persistence of effect of CC-93538 versus placebo for 48 weeks in reducing concomitant corticosteroid use
- To evaluate the time to and frequency of EGE flare events and use of rescue therapy during the study
- To assess trough concentrations of CC-93538 in subjects with EGE

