### Key Secondary Endpoints

- Changes from baseline in each of 5 domain scores of the Izumo Scale
- The proportion of responders defined as subjects who achieve both clinical and histologic response
- Safety and tolerability evaluated by the incidence, severity and relationship to CC-93538 of adverse events (AEs), serious adverse events (SAEs), clinical laboratory abnormalities, changes in vital signs, physical examination abnormalities and the presence of anti-drug antibodies, including neutralizing antibodies when warranted

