For the time-to-event endpoints, the numbers of subjects who have an event will be summarized. The Kaplan-Meier (KM) estimates of the 25th, median, and 75th percentile of the time to the first event and the 2-sided 95% CIs will be provided. The cumulative number of events, the number of subjects at risk, and the KM estimate of the event rate (i.e., failure probability instead of survival probability) and SE will be provided by time point. The KM plot of failure curves (instead of survival curves) with the number of subjects at risk at each time point will be presented. To test the KM curve in the treatment group is different from that in the placebo group in at least one stratum, a stratified log-rank test will be conducted.

Multiplicity Adjustment

Only one formal statistical test will be performed for the primary endpoint. For any other comparisons, nominal p-value (without adjustment for multiplicity) will be provided as a measure of the strength of association between the endpoint and the treatment effect rather than a formal statistical test. Therefore, the multiplicity adjustment is not applicable in this study.

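### The Week 16 key secondary endpoints carry only nominal p-values; a short fixed sequence after the primary would allow an error-controlled conclusion on symptoms at no cost to the primary test

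*Combined protocol and SAP*

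**What the plan says.** The Protocol Summary (Multiplicity Adjustment) and Section 9.6.3.1 carry the same rule. There is one formal test, for the primary endpoint. "For any other comparisons, nominal p-value (without adjustment for multiplicity) will be provided as a measure of the strength of association", and both places conclude: "Therefore, the multiplicity adjustment is not applicable in this study". The primary is judged by the "difference in least squares mean (LSM) at a 5% 2-sided significance level".

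The Protocol Summary and Table 2 also give two efficacy endpoints key secondary status, each at Weeks 16 and 48: change in the five Izumo domain scores, and "The proportion of responders defined as subjects who achieve both clinical and histologic response". Table 2 marks three of the five domains (Gastric Pain, Stomach Heaviness, Diarrhea) as the Symptoms of Interest. The first secondary objective listed is "To assess the efficacy of CC-93538 versus placebo in reducing EGE-related symptoms at Week 16". Safety is a third key secondary and is descriptive.

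No section gives an order of testing or an allocation of alpha for the key secondaries. Section 9.8 plans no formal interim analysis.

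**The concern.** The label of key secondary has no inferential consequence in this plan: these endpoints have the same status as every other secondary comparison. That matters because the primary is a tissue count, while an objective of the trial is symptom efficacy against placebo.

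The protocol's own background shows that the two can diverge. In the Phase 2 EoE study (Section 1.2.2.7), mean change in eosinophil count was -94.76 on 180 mg and -99.90 on 360 mg, against -4.42 on placebo. Mean change in the dysphagia score was -5.31, -13.31 and -6.41 respectively. The lower dose matched the higher on histology but not on symptoms. A histologic success here would therefore not settle the symptom question. As written, the trial could meet its primary, show a clear symptom difference, and still have only an unordered set of nominal p-values for it.

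**Working it through.** **1. The plan's own figure.** Inputs from Section 9.3: "the expected mean change in eos count in the active treatment group was -70", with no change assumed on placebo, SD 70, allocation 2:1, and "the sample size necessary to achieve at least 80% power in a t-test at a significance level of 0.05 was calculated".

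- Standardised effect: 70/70 = 1.0.
- With 26 + 13 = 39, the noncentrality is 1.0/√(1/26 + 1/13) = 2.94 on 37 degrees of freedom, and power is 81.8%.
- With 24 + 12 = 36, power is 78.5%. So 39 is the smallest exact 2:1 total that reaches 80%.
- Dropout: 39/(1 - 0.10) = 43.3, hence 44; the next multiple of 3 is 45, that is 30 + 15.

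The stated 39 and 45 reproduce.

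**2. Reading the key secondaries one by one.** At Week 16 there are 5 domains + 1 composite = 6 comparisons. With no effect and each read at 0.05, the chance of at least one p below 0.05 is 1 - 0.95^6 = 26.5% if they are independent. By simulation with a common correlation:

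| Correlation | Chance of at least one |
|---|---|
| 0 | 26.5% |
| 0.3 | 24% |
| 0.5 | 21% |
| 0.6 | 19% |

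The documents give no correlations; these are assumptions.

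**3. Fixed sequence.** Test the primary at two-sided 0.05, then each listed endpoint at 0.05 in order, stopping at the first failure. The primary is tested exactly as now, so its alpha, N = 39/45 and power (81.8% at 39 evaluable, 87.1% if all 45 are evaluable) do not change. In 400,000 simulated trials with the primary and six secondaries at correlations 0 to 0.7, familywise error was 0.050 when nothing has an effect, and 0.030 to 0.042 when only the primary effect is real.

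**4. What a secondary step could deliver.** The documents give no expected effects, so these are assumed ranges for one test at 0.05 with 30 v 15, before allowing for earlier steps. The composite figures use an unstratified Fisher test, the fallback in Section 9.6.3.1; the planned test is stratified CMH.

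| Composite, active v placebo | Power |
|---|---|
| 30% v 10% | 25% |
| 40% v 10% | 52% |
| 50% v 10% | 76% |
| 60% v 10% | 91% |

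| Domain effect | Power |
|---|---|
| 0.5 SD | 34% |
| 0.8 SD | 70% |
| 1.0 SD | 87% |

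**5. The order matters.** Take the primary at 87%, the composite at 52% (40% v 10%) and a domain at 70% (0.8 SD). If the composite comes first, the chance of reaching and passing the first domain is 0.87 × 0.52 × 0.70 = 32% under independence, rising to about 44% at correlation 0.6. If the domain directly follows the primary, it is 0.87 × 0.70 = 61%, rising to about 66%.

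**The case against.** The strongest reply is that nothing is wrong. One prespecified test at two-sided 5% controls error, and the plan expressly disclaims formal use of every other p-value. The trial has about 45 subjects, is powered only for the primary, and studies a disease the protocol puts at an estimated 500 Japanese patients in 2010. Confining formal inference to the one powered endpoint is defensible. All of this stands, and it is why the point is an improvement and not a correction.

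A reader might infer more than the documents support:

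- *That the plan inflates type I error by 19% to 27%.* It does not. That range applies only if the nominal p-values are read as tests, which the plan says they are not.
- *That a sequence would control error across all key secondary comparisons.* Adding the two regimens v placebo at Week 48 gives 6 + 2 × 6 = 18 comparisons, with a 34% to 60% chance of at least one p below 0.05 under no effect (correlation 0.6 to 0). A Week 16 sequence of four covers only four of them. Across the other 14 the chance remains about 30% to 51%.
- *That symptom evidence rests wholly on the key secondaries, or that they can show nothing.* Table 2 also lists a symptom-only responder endpoint, the EGID Severity Score, time to flare and time to rescue therapy. Section 9.6.3.1 plans estimates and 95% intervals. Only the error-controlled claim is missing.
- *That a formal secondary result is likely.* Power depends entirely on the assumed rates and is modest unless effects are large.

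The reply does not show that the present wording is better. A failed step leaves the remaining endpoints nominal, which is what they are now.

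**Conclusion.** The point holds as a cheap improvement. The plan's primary error control is valid and its text is consistent, but it forgoes an error-controlled answer to its own Week 16 symptom objective when one could be had without touching the primary. Control would extend only to the primary and the endpoints placed in the sequence. The error rates rest on an assumed common correlation. The power figures rest on assumed response rates and effect sizes with all 45 subjects contributing, so they show what is feasible and predict nothing.

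**What to change.** In the Protocol Summary (Multiplicity Adjustment) and Section 9.6.3.1, replace the statement that adjustment does not apply with wording such as: if the primary is significant at two-sided 5%, the following Week 16 comparisons with placebo are tested at two-sided 5% in the order given, stopping at the first p of 0.05 or more; all other comparisons are nominal. A natural list is the composite responder and the three Symptoms of Interest domains. Heartburn, Constipation and every Week 48 comparison stay nominal.

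The sponsor should decide, before unblinding, whether the composite should come first. It also requires a histologic response, so a failure there would block formal testing of every symptom domain behind it.

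The cost is modest but exceeds two sentences. Definitions that would carry a formal test need settling:

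- how gastric and duodenal counts combine in the histologic response;
- the steroid covariate, since Section 9.6.3.1 adjusts for prior steroid use while randomisation is stratified by concomitant use;
- the treatment term, since Section 9.6.3.1 names three groups and only two arms exist at Week 16.

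The amendment follows Section 12.5. No new data, visits or subjects are needed. The downside is that formal claims end at the first failure. If the sponsor keeps the nominal approach, the plan should say that no confirmatory conclusion on symptoms will be drawn.

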### Safety Population

The safety population will consist of all subjects who received at least one dose of IP. The assessment of safety will include AEs, SAEs, AEs leading to discontinuation of study treatment, changes from baseline in laboratory values and vital signs, and incidence and type of laboratory, vital signs, and physical examination abnormalities. Safety data will be summarized by treatment group using descriptive statistics.

Overall safety and tolerability will also be summarized for each drug presentation : the 360 mg dose of CC-93538 administered by two injections of 1.2 mL each at a concentration of 150 mg/mL CC-93538, or by one injection of 2.0 mL at a concentration of 180 mg/mL CC-93538 administered with the PFS device, or by one injection of 2 mL at a concentration of 180 mg/mL CC-93538 administered with the  device utilizing descriptive statistics.

### External Data Monitoring Committee

An external, independent Data Monitoring Committee (DMC) will be convened and will be comprised of physician experts with experience in treating subjects with EGE and a statistician, all of whom are not otherwise involved in the study conduct and for whom there is no identified

conflict of interest. During the study, the DMC will review selected data (to be specified in the DMC charter) on a regular basis for the assessment of benefit-risk and determination of study continuation. An independent third party will prepare the reports of aggregate data summaries and individual subject data listings, as appropriate, for the DMC members for each scheduled meeting. Operational details for the DMC, including a blinding plan to assure that all personnel involved in the conduct of the study remain blinded to the results of data reviews, will also be described in the DMC charter.

## 1 INTRODUCTION

### 1.1 Disease Background

Eosinophilic gastrointestinal disorders (EGIDs) are a series of diseases that selectively affect the segments of the gastrointestinal (GI) tract with eosinophilic inflammation in the absence of secondary causes for eosinophilia. These disorders can be divided into 2 principal groups: eosinophilic esophagitis (EoE) and eosinophilic gastroenteritis (EGE) for infants to adults including the elderly (Rothenberg, 2004; Japan Intractable Diseases Information Center, 2021). Eosinophilic esophagitis is characterized by inflammation in the esophagus, and causes symptoms such as difficulty in swallowing and a feeling of choking, which interfere with activities of daily living due to dysphagia. In long-term cases, it may cause esophageal fibrosis and stenosis. Eosinophilic gastroenteritis is associated with inflammation of the GI tract from the esophagus / stomach to the large intestine, with abdominal pain, nausea, diarrhea, and malnutrition being the major symptoms. Recurrence occurs repeatedly in about 60% of patients, and the disease becomes chronic and steroid-dependent, causing various adverse reactions associated with drug therapy. In Japan, there have been many case reports of EGE, but there are few cases of EoE. In contrast, EoE is more common and EGE is less common in Europe and the United States (US). The prevalence of EGE in Japan is unknown, but EGIDs are estimated to be present in approximately 5000 patients. The number of EGE patients is also unknown but has been estimated as 500 in 2010 (Japan Intractable Diseases Information Center, 2021). The exact prevalence of EGIDs in the US is unknown, but the estimated prevalence of EoE is reported as 56.7/100,000 (Dellon, 2014) and that of EGE is 14.7/100,000 (Jensen, 2016). The prevalence of EGIDs in the US/European Union has been increasing in recent years, and a similar finding has been reported in Japan (Fujishiro, 2011; Kinoshita, 2015; Chehade, 2021). Although eosinophils (eos) are normally present in the lamina propria except the esophagus under noninflammatory conditions, the number of eos along the GI tract is variable, and the highest concentrations are found in the cecum and appendix (Oh, 2008; Ko, 2014). They are involved in the mucosal immune system of the GI tract and have a role in host defense for healthy individuals (Lucendo, 2008). The number of eos increases in the pathogenesis of numerous inflammatory processes, including parasitic infections and allergic diseases. In these states activated eos produce and release highly bioactive inflammatory mediators like eosinophil cationic protein (ECP) and major basic protein. These cationic proteins possessing ribonuclease and antiviral activity are cytotoxic to the GI epithelium. This could trigger degranulation of mast cells and release of cytokines (eg, interleukin (IL)-1, IL-3, IL-4, IL-5, IL-13, transforming growth factors), chemokines (eg, eotaxin, Regulation upon Activation Normal T-cell Expressed and Secreted [RANTES]), lipid mediators (eg, leukotrienes, platelet activating factor), and neuromediators (eg, substance P, vasoactive intestinal polypeptide) (Khan, 2005; Rankin, 2000; Hogan, 2004).
